Primary	Objectives To investigate the potential of retinal imaging technology to assess endothelial function in women during pregnancy, in order to evaluate the effect of GH on maternal CV function.	Outcome Measures Primary Outcome Measures: 1. Retinal Vascular System 2. Endothelial Function 3. Cardiovascular Function biomarkers Secondary Outcome Measures: 1. Pregnancy-Related Health Outcomes 2. Maternal Health
Secondary	Objectives Study – Aim: Investigate whether retinal imaging is able to capture endothelial dysfunction in women who have complicated pregnancy. Endothelial function measured using retinal imaging and ultrasound pulse-wave Doppler and measured in correlation with serum biomarkers.	Outcome Measures 1. Primary Outcome Measures - Retinal Vascular Health measurements - Ultrasound Pulse-Wave Doppler Findings - Blood Biomarkers 2. Secondary Outcome Measures - Long-term Cardiovascular Risk Indicators
Optional Inclusion Criteria	Prospective imaging study 1- Women aged 18 or above 2- Women who are pregnant after 8 weeks 3- Women must be able to give written informed consent (ICF) Note: Women that are diagnosed with gestational hypertension (after 12 weeks) will be included. Includes the following hospital: NINEWELLS HOSPITAL	
Optional Exclusion Criteria	1- Maternal age less than 18 years 2- Women who are not capable of giving informed consent (ICF).	

Studying Pregnancy's VAscular and Retinal Changes (SPARC), Non CTIMP Protocol (SPARC) During Preg <v1.0 13/3/2025>; IRAS: 347685

5.Known retinal or eye disorders	 3- Pre-existing chronic hypertension or cardiovascular diseases diagnosed prior to the index pregnancy. 4. Women that have chronic hypertension at their booking visit (before 12 weeks)
hypertensive therapy, anticoagulants).	5.Known retinal or eye disorders6. Use of medications affecting endothelial function (e.g., ongoing anti-

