1 INTRODUCTION / BACKGROUND & RATIONALE

incident pregnancy.

Hypertensive disorders complicate 6-12% of pregnancies (Khedagi and Bello 2021), leading to PE and intrauterine growth restriction (Di Martino et al. 2022). PE is more commonly associated with adverse maternal and foetal outcomes such as eclampsia, stroke, renal and hepatic dysfunction, foetal growth restriction and stillbirth. According to the most recent Confidential Enquiries into Maternal Death, PE is still one of the most common causes of direct maternal deaths in United Kingdom and is also associated with increased perinatal mortality and morbidity(Shennan et al. 2012). GH is increasing in line with elevated cases of obesity and diabetes in the population (Shah et al. 2008). This is becoming more critically relevant for maternity especially as the obese and diabetic population is increasing in the younger age groups during the reproductive. Hypertensive disorders in pregnancy account for 5% (1:20) of stillbirths with no congenital malformation. Importantly, women who develop PE are also at increased long-term risk of CV disease and stroke (Honigberg et al. 2022). The impact of increased risk of CV disease later in life is under appreciated. Predictions of pregnancies at risk of hypertensive pregnancy will allow stratification of women at most risk, for future and earlier follow up. In addition, this understanding will provide insight into pathological mechanisms. An understanding of when endothelial dysfunction occurs and if it preceeds gestational hypertension will be key to developing diagnostic stratification. Recent studies have suggested that arterial stiffness and endothelial dysfunction may be an important factor in development of GH. Similarly, myocardial impairment and chamber diastolic dysfunction was observed more frequently in GH (a severe form of GH compared with normal pregnancies. These changes in CV function may be present before the clinical onset of GH and are evident after delivery. Therefore, GH seems to be the expression of a

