3.2 STUDY RECRUITMENT

Women will be recruited who are pregnant for assessment in mid and/or late term. The outcome of the pregnancy will be tracked.

Women will be invited to join the study by the care teams in clinics at Ninewells and the Tayside area

- Obstetric Antenatal Clinics (Recruitment will be overseen [name] [name] (UoD/NHS) and [name] (NHS))
- Assisted conception clinic (Recruitment will be overseen [name] [name] (UoD/NHS))
- Hypertension Clinic (Recruitment will be overseen by [name](UoD/NHS))

This is a prospective study. Control groups will be made up of women that do not get gestational hypertension. Pregnant women that attend the Hypertension clinic may be recruited due to their gestational hypertension. Women attending the Obstetric Antenatal Clinics and Assisted conception clinics will be identified with clinical collaborators including [name] [name], [name] and [name]. To be able to identify potential participants from their medical records Caldicott Approval will be sought. Only with Caldicott approval will the medical records be searched.

The care team will approach or invite participation in the study in clinic. Any invitation will introduce the potential patient to the study team and will include a PIS. The care team will not follow up with patients to determine their interest in the study.

The study team will include Clinical Research Centre nurses that will assist with recruitment. The study team will confirm recruitment via a short telephone conversation prior to them attending Ninewells for the study visit.

Advertisement of the study and identification of potential participants will be identified from the NHS Tayside clinics at Ninewells Hospital including maternity clinics, ultrasound department, antenatal clinics, day assessment unit, Assisted Conception Unit, https://www.acudundee.org/ hypertension and diabetics clinics among others. Caldicott approval will be gained to allow identification of potential participants from medical records and clinical lists by the care team. Letters with PIS may be sent to the potential participants from the clinical team. We chose the following sites, since this is where pregnant women obtain their routine care.

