3.3 STUDY DESCRIPTION

At the commencement of the study, the care team will approach pregnant women who meet the criteria. Pregnant women will get a Participant Information

Sheet (PIS) and can reach out to the study team if they wish to participate. Each participant is only required to attend a single visit, which will last roughly 1 hour.

Pregnant volunteers will be recruited at their first (10-12 week) and second (20 weeks) scans in line with their clinical care. In addition to their clinical ultrasounds, an ophthalmic and carotid artery ultrasound will be conducted. In addition a retinal scan and blood sample taken.

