3.4 STUDY FLOWCHART

3.5 STUDY MATRIX

Example Study Matrix

	Recruitm ent	Week 10 (+/-3wk)	Week 20 (+/-3wk)
Recruitment	V1	n/a	n/a
Cardiovascular assessment		X	X
Blood sample		X	Χ
Blood processing		X	Χ

On the same day as the blood sample, carotid artery doppler, and retinal imaging, an ophthalmic artery Doppler will be conducted. In the unlikely event that this is not possible, the ophthalmic artery doppler will be finished in 7 days.

We aim to image women up to 2 times; at 10 and 20 weeks (+/- 3 weeks) in line with their routine clinical care. However, we will accept only one visit at either of the timepoints.

STUDY ASSESSMENTS

Retinal imaging

Retinal imaging is a basic ophthalmic imaging technique which takes a photo of blood vessels at the back of the retinal. The participant needs to open her eyes and stare straight ahead at an object while the image is taken and uploaded to a computer.

Doppler Ultrasound

The ultrasound is a painless, safe test that uses sound waves to make images of the region of interest. Two regions will be examined in this study, which are Ophthalmic and Carotid region.

OPHTHALMIC ARTERY DOPPLER

The participant will be positioned in a supine position and will rest for 5 minutes. Subsequently, an ultrasound probe with sterile conduction gel will be applied to her closed upper eyelid. A quick 2D scan will be undertaken to identify anatomical features of the eye, including the optic nerve, visible as a hypoechoic band, which will be utilised as a reference. The ocular artery will be identified using colour flow, specifically in the superior and medial regions of the artery, around 15 mm behind the optic disc. Subsequently, pulsed-wave Doppler will be employed to document three to five similar waveforms.

To reduce any potential negative impact on the eyes and adhere to the ALARA ("as low as reasonably achievable") guideline, the study will be conducted in under 2 minutes per eye. Both eyes will be imaged.

CAROTID ULTRASOUND

During the test, gel is applied to the side of the neck to help the sound waves travel effectively. While lying down, a small scanner is gently placed on the skin of the neck to take the necessary pictures. This procedure is safe and may cause some pressure, but not pain, as the device moves on the neck.

The elasticity of the blood vessels will also be measured. A small pen-like device will be placed gently on the neck and at the same time a cuff is placed on the thigh (over your clothes).

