6.1 SAMPLE SIZE CALCULATION

Comparison of CV function in women at high and low risk of PE

Ninewells has approximately 4500 births per year with approximately 450 cases of gestational hypertension. Our goal here is to describe the evolution of maternal microvascular function in women that develop gestational hypertension comparing to those that do not develop gestational hypertension.

Our previously published studies (Khan et al 2005 Hypertension, https://doi.org/10.1161/01.HYP.0000186328.90667.95; Changes in Endothelial function preceded the clinical disease in women in whom PE develops) demonstrated changes in microvasculature at 26 weeks in n=15 women with PE compared to normotensive (n=54). Using this previous data, a Power Analysis (G*power)) -A Piori carried out to compute the required sample size for the Wilcoxon-Mann Whitney test (2 groups). With

αα

= 0.05 and power of 95% to detect an effect size of 25%, each group requires a n=11.

As this is a prospective study to obtain measurements at the onset of gestational hypertension, we predict we need to recruit 110 women to obtain the 10% of women that develop gestational hypertension. Women who are high-risk or that have been newly diagnosed, i.e. attending hypertensive clinics, will be recruited

Further details:

 During-Pregnancy: Recruit 110 women to account for the 10% who will develop gestational hypertension.

Sample size required for each group (high vs. low risk):11 women per group

• Total Participants:

-During-Pregnancy: 110 women (recruitment to achieve the final sample of 22 women)

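### Section 6.1 aims to describe the evolution of microvascular function and the primary objective an effect of GH, but the visit rules guarantee no repeat measurement and the scheduled visits fall mostly before GH can begin

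*Protocol*

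**What the plan says.** **Goal.** Section 6.1: "Our goal here is to describe the evolution of maternal microvascular function in women that develop gestational hypertension", set against women who do not develop it. The primary objective, in the synopsis and in section 2 (Table 1), is to study retinal imaging "in order to evaluate the effect of GH on maternal CV function". The background in section 1 gives the motive: "An understanding of when endothelial dysfunction occurs and if it preceeds gestational hypertension will be key" to diagnostic stratification.

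**Visits.** Sections 3.3 and 4.1 both say: "Each participant is only required to attend a single visit, which will last roughly 1 hour". Section 3.5 says: "We aim to image women up to 2 times; at 10 and 20 weeks (+/- 3 weeks"), and its matrix marks both timepoints. It then adds: "However, we will accept only one visit at either of the timepoints". No section sets a minimum number of women measured twice.

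**Timing.** Section 3.2 says: "Women will be recruited who are pregnant for assessment in mid and/or late term". Section 6.1 says: "As this is a prospective study to obtain measurements at the onset of gestational hypertension". Section 9.1 defines GH as new hypertension after 20 weeks. Sections 3.2 and 6.1 also allow recruitment of women from the hypertension clinic because of GH already diagnosed.

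**Analysis.** Section 6.1 sizes the study for a two-group Wilcoxon-Mann-Whitney test. Section 6 names a t-test and logistic regression for comparing groups, and section 6.2 adds correlation and regression.

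**The concern.** Evolution means change over time. With one measurement per woman, a difference between gestational ages is also a difference between women, and a difference between the GH and non-GH groups is a contrast at one time.

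The protocol's own background makes this more than a point of vocabulary. Section 1 suggests that GH may express a cardiovascular syndrome already present before pregnancy. If so, cases and controls would differ at any single visit even if nothing changed during pregnancy. Matching on gestational age would not separate that standing difference from a change in pregnancy or an effect of GH.

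At stake is the conclusion. The data can support an association between microvascular measures and GH status. They need not support a statement about course, and as scheduled they do not support one about what GH does to the vessels.

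**Working it through.** **1. How many repeat measurements are guaranteed.** The minimum under sections 3.3, 3.5 and 4.1 is one visit per woman, so the guaranteed number of the 11 cases with two values is 0. The likely number is higher, since two visits are the aim. The documents give no attendance rate. If 25%, 50% or 75% of cases attended both (assumed), the expected number of pairs among 11 is 11 × 0.25 = 2.75, 11 × 0.50 = 5.5 or 11 × 0.75 = 8.25. Even at 25%, the chance of at least one pair is 1 − 0.75^11 = 0.96. At 75%, the chance that all 11 are paired is 0.75^11 = 0.04.

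**2. Where the visits lie relative to GH.**
- First window: 10 ± 3 = weeks 7 to 13. It closes 20 − 13 = 7 weeks before the earliest onset under section 9.1.
- Second window: 20 ± 3 = weeks 17 to 23. It closes 3 weeks after the earliest onset.
- A pair therefore spans onset only in a woman whose GH begins between weeks 20 and 23 and who is measured after it begins. In all other cases both values precede GH.
- A woman recruited from the hypertension clinic after a diagnosis made beyond week 20 can no longer supply the first value. Only the end of the second window, weeks 20 to 23, is open to her.
- The synopsis speaks of GH diagnosed after 12 weeks, which differs from section 9.1. These timing statements rest on section 9.1.

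**3. What the stated sample size is for.** The protocol gives 11 per group, α = 0.05, power 95% and an effect size of 25%. The 11 cannot be confirmed, because neither the scale of the 25% nor a standard deviation (SD) is given. Read as a standardised difference of 0.25, about 437 per group would be needed (two-sided, normal data). For 11 to suffice, the standardised difference must be about 1.66 two-sided or 1.49 one-sided. That is a separate issue. What matters here is that every reading uses one value per woman in two independent groups, and none sizes a change.

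**4. Cost of single visits for estimating change (illustration only).** The within-woman correlation ρ is not in the documents, so 0.3 to 0.9 is assumed, with equal SD at both visits. Standard errors (SE) are in SD units, for mean change in 11 cases.

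- Paired, all 11 seen twice: SE = √(2(1 − ρ)/11).
- Seen once each, 5 at one timepoint and 6 at the other: SE = √(1/5 + 1/6) = √0.3667 = 0.606.

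| ρ | Paired SE | Ratio, single to paired |
|---|---|---|
| 0.3 | √(1.4/11) = 0.357 | 1.7 |
| 0.5 | √(1.0/11) = 0.302 | 2.0 |
| 0.7 | √(0.6/11) = 0.234 | 2.6 |
| 0.9 | √(0.2/11) = 0.135 | 4.5 |

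Section 6.1 compares groups, so the relevant quantity is the difference in change. With 11 controls measured in the same way, each SE is multiplied by √2: at ρ = 0.5, about 0.43 against 0.86. The ratios do not change. The single-visit estimate also requires that the women seen early and those seen later be exchangeable. If all cases attend at the same timepoint, there is no estimate of change.

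**The case against.** Much of the protocol is already between-group. The sentence in 6.1 goes on to a comparison with women who do not develop GH. The section 2 hypothesis concerns a difference between women, and the sizing and named tests follow it. On that view, evolution is a loose word in a sample-size preamble, the remark on timing in section 1 is background only, and accepting one visit is an ordinary allowance for incomplete attendance. An effect of an exposure can also be addressed by an adjusted between-group comparison under assumptions, and sections 6 and 6.2 plan adjustment. A change analysis might be set out in a statistical analysis plan that is not at hand.

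Most of this stands, and it limits the point. The cross-sectional comparison remains usable, and the lack of a named change analysis is not itself the fault. But the goal and the visit requirement are both fixed in the protocol, and they do not match. No later plan can analyse repeat measurements that were not required.

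Three stronger readings are not supported:
- **That there will be no paired data.** Two visits are the stated aim and the matrix marks both, so some pairs are likely.
- **That making both visits compulsory would justify an effect of GH.** The second window closes at week 23, so most pairs would precede onset.
- **That an effect of GH can only ever be a within-woman question.** The difficulty is narrower: measurements taken mostly before GH begins cannot show its effect, whether paired or not, and women measured once after onset leave a pre-existing difference unseparated.

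**Conclusion.** The point holds as a mismatch between the stated goal and the data the protocol secures. Evolution need not be observable in any woman, and an effect of GH is not supported by this schedule under either visit rule. Two visits could describe the course up to mid-pregnancy in the women who have both, and no more.

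The loss of precision, about 1.7 to 4.5 times in the SE of mean change, illustrates an unfavourable case: no case is paired and ρ is assumed to lie between 0.3 and 0.9. It is not a forecast. The timing argument depends on section 9.1 placing onset after 20 weeks. The between-group comparison survives, so this calls for correcting the claim, not abandoning the design.

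**What to change.** 1. In section 6.1 and the primary objective (synopsis and Table 1), restate the goal as a between-group comparison, that is an association, of microvascular function at a stated timepoint in women who do and do not develop GH. Drop the effect-of-GH wording whichever visit rule is kept.
2. Limit any statement about evolution to within-woman change between the two visits, compared between groups, in women who have both. Report how many there are. Women seen once enter only the cross-sectional comparison at their own timepoint.
3. Reconcile the visit statements in sections 3.3, 3.5 and 4.1. Reconcile also the assessment timing: weeks 10 and 20 in 3.5, mid-to-late pregnancy in sections 2, 3.2 and 3.14, and onset of GH in 6.1. The synopsis and section 9.1 also need to agree on when GH can be diagnosed.

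**Cost.** These are wording changes, though section 11.1 requires sponsor, ethics committee and NHS R&D approval for an amendment. The stated goal becomes narrower, and the change analysis will probably rest on few women. Compulsory second visits are not needed for this fix. They would yield more pairs, but would reverse the single-visit rule and add imaging and a further 20 ml blood sample for women now seen once. The sponsor would have to weigh that trade-off.

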3 STUDY DESIGN

The study design is a prospective study, as it examines endothelial function in pregnant women and see how this relates to the potential development of gestational hypertension.

Study Aim: Imaging the retina in mid-stages of gestation and tracking pregnancy outcomes in correlation with serum biomarkers and for standard diagnostic measurement (ultrasound pulse-wave Doppler) imaging.

 Pregnant women will be recruited at the normal pre-natal visits (early and mid gestation scans)

- Blood samples will be taken in addition to bloods take in line with routine care (early 10-12 week scan). 20-week scan women will be requested to provide blood samples. (sFlt-1 &PLGF (clinically used to diagnose PE), endothelin-1 (marker of endothelial dysfunction))
 - Recruit women who are pregnant and follow pregnancy outcome
 - Recruit women who have gestational hypertensionGH and gestational-matched normal tensive women for CV assessment.
 - Endothelial CV assessment.
 - Retinal imaging
 - Blood sample (sFlt-1 &PLGF (clinically used to diagnose PE), endothelin-1 (marker of endothelial dysfunction))
 - Ultrasound
 - Carotid
 - Ophthalmic artery doppler

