3.14 INCLUSION CRITERIA

Case group:

Women who

- Are Aged 18 or above
- Are Able to give written informed consent (ICF)
- Are in mid-to-late gestation.
- Were diagnosed with Gestational hypertension (systolic BP ≥ 140 mmHg or diastolic BP ≥ 90 mmHg) in their pregnancy.
- Do not have cardiac or ophthalmic disorders

Control group:

Pregnant women that are

- Aged 18 or above
- Able to give written informed consent (ICF)
- Have no gestational hypertension (normal pregnancy/ nonhypertension)
- Do not have cardiac or ophthalmic disorders

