9 ADVERSE EVENTS

Serious Adverse A serious adverse event is any untoward medic occurrence that:	Adverse Event (AE)	Any untoward medical occurrence in a clinical research participant which does not necessarily have a causal relationship with study participation
existing hospitalisation		 results in death is life threatening requires hospitalisation or prolongation of existing hospitalisation results in persistent or significant disability or incapacity

9.1 **DEFINITIONS**

The following definitions will be used in this study, based on the American College of Obstetrics and Gynaecology (ACOG, 2002).

- 1- Chronic hypertension: BP ≥140/±90 mm Hg before pregnancy or before the 20th week of gestation
- 2- Preeclampsia-eclampsia: A pregnancy-specific disorder that is a multisystem disease characterized by hypertension ≥140/±90 mm Hg on ≥2 occasions at least 6 hours apart, and proteinuria ≥300 mg in a

24-hour urine collection, after 20 weeks' gestation. The convulsive form of PE is eclampsia and affects 0.1% of all pregnancies.

- 3- Preeclampsia superimposed on chronic hypertension: Up to 30% of women with chronic hypertension develop PE, as heralded by the occurrence of de novo proteinuria in the third trimester. In women with chronic hypertension and preexisting proteinuria (ie, before 20 weeks of gestation), the diagnosis of superimposed PE is likely with any of the following findings: sudden increase in proteinuria, sudden worsening of previously well-controlled BP, new-onset thrombocytopenia, or elevated liver function tests.
- 4- Gestational hypertension: New onset of hypertension ≥140/±90 mm Hg on ≥2 occasions at least 6 hours apart, after 20 weeks' gestation, in the absence of proteinuria, <300 mg in a 24-hour urine collection. If BP returns to normal by 12 weeks postpartum, the diagnosis of transient hypertension of pregnancy can be assigned. If elevated BP persists, the diagnosis of chronic hypertension is made.

Other conditions:

Pre-gestational diabetes

- Type I insulin-requiring diabetes
 - Participant taking (or prescribed) insulin prior to pregnancy
- Type II non-insulin requiring diabetes
 - Participant taking (or prescribed) oral diabetic agents prior to pregnancy

Gestational diabetes

- Prior pregnancy affected by gestational diabetes
 - No interval diagnosis of diabetes
- Current pregnancy affected by gestational diabetes

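### Scan timing is contradictory (10 and 20 weeks, onset of gestational hypertension, or mid-to-late gestation), and pre-onset and post-diagnosis cases share one group, so case status can be confounded with gestational age at scan

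*Protocol*

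**What the plan says.** **Schedule.** Section 3.5: "We aim to image women up to 2 times; at 10 and 20 weeks (+/- 3 weeks) in line with their routine clinical care". It then adds: "However, we will accept only one visit at either of the timepoints". Sections 3.3 and 4.1 require a single visit per participant.

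**Intended time of measurement.** Section 6.1: "As this is a prospective study to obtain measurements at the onset of gestational hypertension". Section 9.1 defines GH as new hypertension "on ≥2 occasions at least 6 hours apart, after 20 weeks". Tables 1 and 2 in Section 2 give mid-to-late pregnancy (printed as mild-late) as the timepoint for both groups, and Section 3.2 speaks of assessment in mid and/or late term.

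**Who is a case.** Section 3.14 lists, for cases only, "Are in mid-to-late gestation", together with an existing GH diagnosis. Section 3.12 enrols pregnant women generally and assigns the two groups retrospectively by outcome. Section 6.1 adds a second route: "Women who are high-risk or that have been newly diagnosed, i.e. attending hypertensive clinics, will be recruited". Section 3.13 has one case group of 11 and one control group of 11.

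**Control of gestational age.** Section 3 refers to recruiting "gestational-matched normal tensive women for CV assessment". Section 6 plans a t-test and logistic regression, the latter to account for confounders. Section 6.2 gives maternal age, BMI and pre-existing conditions as examples of confounders.

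**The concern.** The sections cannot all be followed. A woman whose GH begins after week 23 cannot be measured at onset on the stated schedule, and a woman recruited from the hypertension clinic after that week has no visit window at all.

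The case group also mixes two kinds of woman. Those enrolled early and classified later are mostly scanned before GH, and they bear on whether endothelial dysfunction precedes the disease (Sections 1 and 3). Those recruited after diagnosis bear on the effect of GH on maternal cardiovascular function, which is the primary objective in Table 1. A pooled contrast is a weighted mixture of the two, with weights set by how recruitment happens to go.

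If the post-diagnosis cases are scanned later in pregnancy than the controls, any retinal, Doppler or biomarker measure that changes with gestation will differ between groups without any effect of GH. Scan timing cannot be repaired at analysis. With 22 women and little overlap in gestational age, a covariate would have to extrapolate.

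**Working it through.** **1. The plan's own recruitment figure.** Inputs from Section 6.1: 11 cases needed, 10% incidence. 11 / 0.10 = 110, as stated. This holds only if all 11 cases arise within the cohort. If k cases come from the hypertension clinic, the same logic gives (11 − k) / 0.10; for k = 5 that is 6 / 0.10 = 60. So 110 presumes one type of case, while the text beside it recruits two.

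**2. Scan windows against onset.** From Section 3.5: 10 ± 3 gives weeks 7–13; 20 ± 3 gives weeks 17–23. From Section 9.1: onset after week 20. The overlap is about weeks 20–23.

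**3. What the text allows for each group.**

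| | Cases | Controls |
|---|---|---|
| Gestation criterion (3.14) | mid-to-late | none |
| Scheduled scans (3.5) | weeks 7–13 and/or 17–23 | weeks 7–13 and/or 17–23 |
| After week 23 | implied by 3.14, 3.2 and 6.1 | no scheduled visit |
| Matching window | not stated | not stated |

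A control may therefore contribute only a scan at 7–13 weeks, and a case scanned after week 23 has no scheduled control at the same gestation.

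**4. Possible size (assumptions, not figures from the protocol).** The protocol gives no gestational trend. Let s be the share of cases scanned late, g the gap in weeks and b the drift in SD per week. With no true effect the spurious standardised difference is d = s × g × b. The false-positive rate is the power at d of a two-sided 5% two-sample t-test with 11 per group: noncentrality d × √(11/2), 20 degrees of freedom, critical value 2.086.

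| s | g (weeks) | b (SD/week) | d | Noncentrality | False-positive rate |
|---|---|---|---|---|---|
| any | 0 (matched) | any | 0 | 0 | 5% |
| 0.5 | 10 | 0.02 | 0.10 | 0.23 | 5.6% |
| 0.5 | 10 | 0.05 | 0.25 | 0.59 | 8.6% |
| 0.5 | 10 | 0.10 | 0.50 | 1.17 | 20.1% |
| 1 | 12 | 0.05 | 0.60 | 1.41 | 26.8% |

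Using a Wilcoxon test, as in the sizing, changes little: the three rows with s = 0.5 become 5.5%, 8.5% and 19%.

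**The case against.** The strongest reply is that the protocol does address gestational age. Section 3 names gestational matching, and Tables 1 and 2 give both groups the same timepoint. Section 6 plans regression to account for confounders, and the covariates in Section 6.2 are examples, so gestational age is not excluded; exact covariates are commonly left to an analysis plan. Retrospective grouping does not prevent matching either: of 110 women at 10% incidence, about 110 × 0.90 = 99 would be without GH, enough to choose 11 controls by gestation at scan. All of this stands. Its limit is that selection from the cohort works only up to week 23, and that no section says it will be done.

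A reader might go further and infer that case status *is* confounded with gestational age. The documents do not support that, given the matching and the shared timepoint. A reader might also infer that measurement at onset is impossible on the schedule. Weeks 20–23 overlap, and the synopsis admits GH diagnosed after 12 weeks, so that is too strong as well.

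Larger error rates can be produced by assuming that cases are scanned on average 12 weeks later than controls: 0.03–0.10 SD per week then gives d = 0.36–1.2 and about 13–76%. That gap fits poorly with a mixed case group. If half the cases follow the controls' schedule, the other half would need a gap of 24 weeks: week 20 + 24 = 44 against week-20 controls, or week 15 + 24 = 39 against an even mix of 10- and 20-week scans. The upper end should not be used to judge the point.

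**Conclusion.** The point holds as an internal contradiction with an unresolved risk of bias. Two parts rest on the text alone: the 10/20-week schedule does not fit measurement at onset or in late gestation, and pre-onset and post-diagnosis cases are pooled without distinction. The third part, confounding with gestational age at scan, is possible rather than established, because matching is named but not made operational.

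Its size cannot be derived from the protocol. If the measures drift with gestation enough to create a spurious difference of 0.25–0.6 SD, the false-positive rate at 11 versus 11 is about 9–27% instead of 5%. The upper figure requires all cases to be scanned 12 weeks later than controls; with half of them 10 weeks later, 0.05–0.10 SD per week gives about 9–20%. With effective matching there is no bias from this source. The contradiction should be resolved before recruitment, since scan times are fixed once the visit has taken place.

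**What to change.** - Reconcile Section 2 (Tables 1 and 2), Section 3 and Sections 3.2, 3.3, 3.5, 3.14 and 6.1 on when each group is scanned. Which statement gives way is for the sponsor to decide.
- Apply the same gestational window to cases and controls in Section 3.14. Compare cases only with controls imaged within a stated distance of the same gestation, for example ±2 weeks.
- Record gestational age at scan and name it as a covariate in the group comparisons.
- Analyse and report pre-onset and post-diagnosis cases separately, and state which comparison serves the primary objective.

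The wording changes and the covariate cost little, since gestation should be known at each scan. The real costs are fewer cases in each comparison than the planned 11, so the sample size statement must say which comparison it supports, and controls for cases scanned after week 23 whose single visit falls at a matched week, which the present matrix does not provide.
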